8.4 Analysis Populations:8.4.1. Safety Population

All patients who receive at least 1 dose of the combination therapy will be included in the analysis of safety regardless of the duration of treatment. Patients who experience adverse events during the screening period but who do not start on study treatment due to reasons that include, but are not limited to ineligibility/screen failure, death or withdrawal of consent, will not be included in the safety population.

8.4.2. Efficacy Evaluable Population

All patients who complete at least one post-baseline disease status assessment or who discontinue study medication early due to study drug-related toxicity will be considered evaluable for efficacy. Patients who do not meet the aforementioned requirements will be considered non-evaluable for response and may be replaced.

In addition, we will perform a sensitivity analysis for the efficacy endpoint which will include all patients who have received at least one dose of the study treatment (i.e., those who drop off study early due to any reason will be counted as non-responders).

8.4.3. DLT-evaluable population:

Unless doses are missed in Cycle 1 due to DLT(s), a patient must receive at least 70% of the planned doses of venetoclax and omacetaxine to be considered evaluable for DLT. If a patient received fewer doses/days of treatment in the first cycle of treatment for reasons other than a DLT, the patient will be considered non-evaluable for DLT and replaced.

8.5 Analysis Plan:

Descriptive statistics including plots, mean, median and standard deviations will be used to summarize data. For the primary efficacy analysis, we will estimate the ORR for the combination treatment, along with the Bayesian 95% credible interval. The priors for ORR will be (0.2, 0.8) for AML cohort and (0.15, 0.85) for MDS cohort. Event-free survival (EFS) is defined as the time interval between the date of treatment start and the date of [treatment failure, relapse or death from any cause](#). The Kaplan-Meier method will be used to estimate the probabilities of event-free survival (EFS) and overall survival (OS). Log-rank tests will be used to compare among subgroups of patients in terms of EFS or OS. Similar analyses will be performed for the duration of response. MRD negative status and exploratory biomarkers will be summarized graphically and with descriptive statistics. The association between molecular and cellular markers and overall response and/or resistance will be assessed through logistic regression analyses. Paired t-test or Wilcoxon signed rank test will be used to assess the marker change over time. Safety data will be summarized using frequency and percentage, by category and severity.

The Investigator is responsible for completing an efficacy/safety summary report, and submitting it to the IND Office Medical Affairs and Safety Group, for review and approval

- Phase 1b

After the first 3 evaluable patients, per arm, complete 1 cycle of study treatment, and every 3 evaluable patients thereafter, IND Office approval must be obtained prior to advancing/changing dose levels.

- Phase 2:

After the first 10 evaluable patients, per arm, complete 3 cycles of study treatment, and every 10 patients thereafter.

A copy of the cohort summary should be placed in the Investigator's Regulatory Binder under "sponsor correspondence".

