Analyses of overall response rate (ORR) as defined by CR + CRi + PR + MLFS, CR rate, CR/CRi rate, CR/CRh rate will be performed for enrolled subjects, with laboratory response assessment occurring +/- 7 days from bone marrow evaluations. The depth of remission such as with exploratory analyses of MRD negativity by flow cytometry and/or concomitant molecular analysis will also be performed.

6.1.2 Primary Efficacy Analysis: Clinical activity assessed based on revised IWG Response Criteria for MDS (Cheson et al., 2006)

The primary endpoint is the overall response rate (ORR), defined as the proportion of patients who had CR (complete remission), PR (partial response), Hematologic Improvement, or mCR (marrow clearance of blasts) within 3 months of treatment initiation among adult patients with MDS.

CR: Absolute neutrophil count $> 10^3/\mu\text{L}$, platelets $\geq 10^5/\mu\text{L}$, hemoglobin $\geq 11 \text{ g/dL}$, and bone marrow with $< 5\%$ blasts. Peripheral dysplasia will be noted.

PR: All of the hematologic values for a CR, but with a decrease of at least 50% in the percentage of blasts, to 5% to 25%, in the bone marrow aspirate.

mCR Bone marrow with $< 5\%$ blasts and decrease by $\geq 50\%$ over pretreatment, no hematologic recovery required.

HI Improvement in neutrophil count, platelets, or red cells (see below)

SD Failure to achieve at least PR, but no evidence of progression for > 8 weeks

Analyses of overall response rate (ORR) as defined by CR + PR + mCR + HI, CR rate, will be performed for enrolled subjects, with laboratory response assessment occurring $+\text{-} 7$ days from bone marrow evaluations. The depth of remission such as with exploratory analyses of MRD negativity by flow cytometry and/or concomitant molecular analysis will also be performed.

6.1.3. Hematologic Improvement Response Criteria:

*Responses must last at least 8 weeks

Proposed Modified International Working Group Response Criteria for Hematologic improvement*	Response criteria (Responses must last at least 8 weeks)†
Erythroid response (pretreatment, $< 11 \text{ g/dL}$)	Hgb increase by $\geq 1.5 \text{ g/dL}$ Relevant reduction of units of RBC transfusions by an absolute number of at least 4 RBC transfusions/8 wk compared with the pretreatment transfusion number in the previous 8 wk. Only RBC transfusions given for a Hgb of $\leq 9.0 \text{ g/dL}$ pretreatment will count in the RBC transfusion response evaluation†

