After Phase 1b part of the trial is completed, select the MTD for each arm based on isotonic regression as specified in Liu and Yuan (2015). This computation is implemented by the shiny app "BOIN" available at <http://www.trialdesign.org>. Specifically for each arm, select as the MTD the dose for which the isotonic estimate of the toxicity rate is closest to the target toxicity rate. If there are ties, select the higher dose level when the isotonic estimate is lower than the target toxicity rate and select the lower dose level when the isotonic estimate is greater than or equal to the target toxicity rate. Furthermore, the RP2D will be selected based on safety and efficacy, in Arms A and B independently.

Operation Characteristics

Table 3 shows the operating characteristics of the Boin design based on 1000 simulations using shiny app "BOIN" available at <http://www.trialdesign.org>. The operating characteristics show that the design selects the true MTD, if any, with high probability and allocates more patients to the dose levels with the DLT rate closest to the target of 0.3.

Table 3. Operating characteristics of the Boin design (Dose 0 is the starting dose)

	Dose Level -2	Dose Level -1	Dose Level 0 (starting dose)	Dose Level 1	Number of Patients	% Early Stopping
Scenario 1						
True DLT Rate	0.47	0.55	0.64	0.75		
Selection %	44.2	27.6	8.2	0.1		19.9
% Pts Treated	24.4	36	37.7	1.9	11.8	
Scenario 2						
True DLT Rate	0.11	0.3	0.47	0.67		
Selection %	9.1	52.5	34.3	3.2		0.9
% Pts Treated	5.8	33.8	52	8.4	11.8	
Scenario 3						
True DLT Rate	0.02	0.13	0.3	0.47		
Selection %	0.3	19.3	54.5	25.6		0.3
% Pts Treated	0.4	15.7	58.1	25.9	11.7	
Scenario 4						
True DLT Rate	0.05	0.1	0.15	0.3		
Selection %	0	2.4	26.6	71		0
% Pts Treated	0	3.1	43.8	53.2	11.9	

Phase II:

In phase II portion of the study, patients will be treated at the RP2D level chosen during phase 1b for each arm separately. A maximum of 30 patients will be treated in each arm. For AML patients, the primary efficacy endpoint is overall response, defined as CR, CRh, CRi, PR or marrow clearance of blasts within 3 cycles of treatment. For MDS patients, the primary efficacy endpoint is overall response, defined as CR, PR, HI (Hematologic Improvement), or mCR (marrow clearance of blasts) within 3 cycles of treatment. In addition, we will continue to monitor the DLTs that occurred during the first 3 cycles of treatment.

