For each arm, the efficacy and toxicity will be monitored simultaneously using the Bayesian optimal phase 2 (BOP2) design (Zhou, Lee and Yuan, 2017). Specifically, let n denote the interim sample size and N denote the maximum sample size. Let Y_{eff} and Y_{tox} denote the binary efficacy and toxicity endpoints, with $Y_{eff} = 1$ and $Y_{tox} = 1$ indicating that patients experience efficacy and toxicity, respectively. We assume that the joint distribution of (Y_{eff}, Y_{tox}) follows a multinomial distribution with four elementary outcomes: $(Y_{eff}, Y_{tox}) = (1, 1), (1, 0), (0, 1)$ and $(0, 0)$. Let $\mathbf{p} = (P_{11}, P_{10}, P_{01}, P_{00})$ denote the probabilities of observing the four outcomes, and let $p_{eff} = Pr(Y_{eff} = 1)$, $p_{tox} = Pr(Y_{tox} = 1)$ and $p_{efftox} = Pr(Y_{eff} = 1, Y_{tox} = 1)$.

AML Arm:

The treatment is deemed unacceptable if $p_{eff} \leq 0.2$ or $p_{tox} > 0.2$. Thus, we will stop enrolling patients and claim that the treatment is unacceptable if

$$Pr(p_{eff} > 0.2 | data) < \lambda \left(\frac{n}{N} \right)^\alpha,$$

or

$$Pr(p_{tox} \leq 0.2 | data) < \lambda \left(\frac{n}{N} \right)^{\alpha/3},$$

where $\lambda=0.5$ and $\alpha=0.51$ are design parameters optimized to maximize the study power, i.e., probability of correctly concluding an efficacious and safe treatment as acceptable when $p_{eff} = 0.4$, $p_{tox} = 0.1$ and $p_{efftox} = 0.04$, while controlling that the probability of incorrectly claiming an ineffectual and toxic treatment, i.e., type I error, with $p_{eff} = 0.2$, $p_{tox} = 0.2$ and $p_{efftox} = 0.04$, to 10.4%. Note that in the safety stopping rule, the original publication of the design used the probability cutoff $\lambda(n/N)^\alpha$, here the attenuation factor 3 is added (i.e., $\alpha/3$) to obtain stricter interim stopping boundaries to enhance safety.

This optimization is performed assuming a vague Dirichlet prior $Dir(0.04, 0.16, 0.16, 0.64)$ for \mathbf{p} . The prior is chosen such that it corresponds to a prior effective sample size of 1 patient, and the prior estimates of p_{eff} and p_{tox} match the values specified when the treatment is unacceptable. The above decision rule leads to the following optimal stopping boundaries, in cohort size of 6.

Table 4: Optimized stopping boundaries for AML Arm

# patients treated	Stop if # response <=	OR # toxicity >=
6	0	2
12	1	3
18	3	4
24	4	6
30	6	7

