When the total number of AML patients reaches the maximum sample size of 30, we conclude that the treatment is acceptable if the number of responses are greater than 6, and the number of toxicities are less than 7; otherwise we conclude that the treatment is unacceptable. The go/no-go criteria in Table 4 are non-binding.

Below are the operating characteristics of the design based on 10000 simulations using the BOP2 web application (BOP2 V1.4.7.0), which is available at <http://www.trialdesign.org>.

Table 5: Operating characteristics for the interim futility and toxicity monitoring in AML Arm

Scenario	Pr(Eff)	Pr(Tox)	Pr(Eff & Tox)	Early Stopping (%)	Claim Acceptable (%)	Average Sample Size
1	0.20	0.20	0.040	85.03	10.44	12.8
2	0.40	0.10	0.040	25.31	73.93	24.8
3	0.40	0.25	0.120	80.66	15.88	13.4
4	0.15	0.30	0.045	98.07	0.77	8.5

MDS Arm:

The treatment is deemed unacceptable if $p_{eff} \leq 0.15$ or $p_{tox} > 0.2$. Thus, we will stop enrolling patients and claim that the treatment is unacceptable if

$$Pr(p_{eff} > 0.15 | data) < \lambda \left(\frac{n}{N} \right)^\alpha,$$

or

$$Pr(p_{tox} \leq 0.2 | data) < \lambda \left(\frac{n}{N} \right)^{\alpha/3},$$

where $\lambda=0.52$ and $\alpha=0.15$ are design parameters optimized to maximize the study power, i.e., probability of correctly concluding an efficacious and safe treatment as acceptable when $p_{eff} = 0.3$, $p_{tox} = 0.1$ and $p_{efftox} = 0.03$, while controlling that the probability of incorrectly claiming an ineffectual and toxic treatment, i.e., type I error, with $p_{eff} = 0.15$, $p_{tox} = 0.2$ and $p_{efftox} = 0.03$, to 9.8%. Note that in the safety stopping rule, the original publication of the design used the probability cutoff $\lambda(n/N)^\alpha$, here the attenuation factor 3 is added (i.e., $\alpha/3$) to obtain stricter interim stopping boundaries to enhance safety.

This optimization is performed assuming a vague Dirichlet prior $Dir(0.03, 0.12, 0.17, 0.68)$ for \mathbf{p} . The prior is chosen such that it corresponds to a prior effective sample size of 1 patient, and the prior estimates of p_{eff} and p_{tox} match the values specified when the treatment is unacceptable. The above decision rule leads to the following optimal stopping boundaries, in cohort size of 6.

Table 6: Optimized stopping boundaries for MDS Arm

# patients treated	Stop if # response \leq	OR # toxicity
		\geq
6	0	2
12	1	3
18	2	4
24	3	5
30	4	7

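### The plan does not fix one population or one response window for the primary ORR, and Section 8.4.2 lets treated but unassessed patients be dropped and replaced, which can raise the ORR

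*Combined protocol and SAP*

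**What the plan says.** **Population.**

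- Sections 6.1.1 (AML) and 6.1.2 (MDS) say the ORR analyses "will be performed for enrolled subjects".
- Section 8.0, Phase II, indexes the stopping boundaries by "patients treated" and sets a cap: "A maximum of 30 patients will be treated in each arm". A final rule is printed only at 30. For AML it begins "When the total number of AML patients reaches the maximum sample size of 30, we conclude that the treatment is acceptable" and requires more than 6 responses and fewer than 7 toxicities. For MDS it requires more than 4 responses and fewer than 7 toxicities.
- Section 8.4.2 defines an efficacy-evaluable set: at least one post-baseline disease assessment, or early discontinuation for drug-related toxicity. Of everyone else it says: "Patients who do not meet the aforementioned requirements will be considered non-evaluable for response and may be replaced". It adds a sensitivity analysis of all dosed patients in which "those who drop off study early due to any reason will be counted as non-responders".
- Section 8.5 says "For the primary efficacy analysis, we will estimate the ORR for the combination treatment", with a 95% credible interval, and names no analysis set.
- The Phase 2 summary report at the end of 8.5 is triggered by yet another count: "After the first 10 evaluable patients, per arm, complete 3 cycles of study treatment".

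**Window.** Sections 6.1.1 and 6.1.2 count responses within 3 months of starting treatment. Section 8.0 counts them within 3 cycles. Section 4.3 sets cycles of 4 to 6 weeks, with longer delays possible.

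**The concern.** Because the all-treated analysis is labelled a sensitivity analysis, the reader infers that the evaluable set is primary, but the plan never says so. The set favours the treatment. A treated patient who dies, progresses or withdraws before any assessment, for a reason other than drug-related toxicity, is removed and may be replaced. Such a patient cannot be a documented responder. The first planned marrow is at day 28 (±7) in 5.2.4, so early failures can fall in this gap. Section 5.2.4 lets progression be established from blood without a marrow, but 8.4.2 does not say whether that counts as an assessment.

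The rule also sits badly with the design. Replacing up to 30 evaluable patients exceeds the cap of 30 treated. If any patient is non-evaluable and not replaced, the evaluable count never reaches 30, where the final rule applies.

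At stake are the reported ORR and the go/no-go reading against 20% or 15%. The plan does not say whether those null rates refer to treated or evaluable patients.

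**Working it through.** **Reproducing the plan.** Inputs are the priors, λ, α and stopping rules in 8.0. Each boundary comes from the beta marginal of the stated Dirichlet prior: Beta(0.2, 0.8) for AML response, Beta(0.15, 0.85) for MDS response and Beta(0.2, 0.8) for toxicity. The cutoff is λ(n/30)^α for response and λ(n/30)^(α/3) for toxicity. All ten boundary pairs reproduce. Exact enumeration over looks at 6, 12, 18, 24 and 30 gives these chances of claiming acceptable:

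| Arm | Null, exact (plan) | Alternative, exact (plan) |
|---|---|---|
| AML | 10.25% (10.44%) | 74.05% (73.93%) |
| MDS | 9.25% (9.77%) | 64.96% (65.36%) |

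The null differences are within the error of 10,000 simulations (standard error about 0.3 points). The printed figures are not in dispute. The question is which patients they count.

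**Same data, two counts, within the 30-treated cap.** Assume 6 of 30 treated patients are unassessed.

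- AML, 6 responses. As treated, 6/30 = 20.0%, which is unacceptable (≤6 at 30). As evaluable, 6/24 = 25.0%, which is not stopped (≤4 at 24). By formula, Pr(p>0.2) = 0.464 < 0.50 at 30, and 0.691 > 0.5×(24/30)^0.51 = 0.446 at 24.
- MDS, 4 responses. As treated, 4/30 = 13.3%, which is unacceptable (≤4 at 30). As evaluable, 4/24 = 16.7%, which is not stopped (≤3 at 24). By formula, Pr(p>0.15) = 0.351 < 0.52 at 30, and 0.539 > 0.52×(24/30)^0.15 = 0.503 at 24.

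With only 3 unassessed, AML still flips: 6/27 gives 0.576 > 0.5×(27/30)^0.51 = 0.474. MDS does not: 4/27 gives 0.440 < 0.52×(27/30)^0.15 = 0.512.

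**Full replacement.** Let f be the fraction of treated patients who are excluded non-responders, all of them replaced, and let the null rate p0 apply to all treated patients. The evaluable ORR is then p0/(1−f), and the number treated to reach 30 evaluable is 30/(1−f). Response and toxicity are taken as independent. Three toxicity assumptions were run:

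- (a) toxicity stays at 0.20 among evaluable patients;
- (b) excluded patients carry no toxicity, so evaluable toxicity is 0.20/(1−f);
- (c) as (b), but for a safe, inactive regimen, 0.10/(1−f). The plan does not tabulate this case.

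| | f = 0 | 5% | 10% | 20% |
|---|---|---|---|---|
| Treated for 30 evaluable | 30 | 31.6 | 33.3 | 37.5 |
| AML evaluable ORR | 20.0% | 21.1% | 22.2% | 25.0% |
| AML P(acceptable), (a) | 10.25% | 11.9% | 13.8% | 18.1% |
| AML, (b) | 10.25% | 10.4% | 10.4% | 9.1% |
| AML, (c) | 23.5% | 26.6% | 29.8% | 36.1% |
| MDS evaluable ORR | 15.0% | 15.8% | 16.7% | 18.8% |
| MDS P(acceptable), (a) | 9.25% | 10.4% | 11.7% | 14.7% |
| MDS, (b) | 9.25% | 9.0% | 8.6% | 7.0% |
| MDS, (c) | 23.0% | 25.1% | 27.2% | 31.1% |

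Only the change from the f = 0 column is due to the replacement rule.

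**Window.** Three cycles of 4, 5 or 6 weeks last 84, 105 or 126 days. Three months is about 91 days. With 4-week cycles, a response on days 85–91 counts in Section 6 but not in Section 8. With 5- or 6-week cycles, a response from day 92 to day 105 or 126 counts in Section 8 but not in Section 6.

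**The case against.** Several points on the other side are right and limit the concern.

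- The go/no-go criteria are stated to be non-binding in both arms, so a changed count does not force a changed decision. It still leaves open which ORR is reported as primary.
- The all-treated analysis is already planned, and patients who stop for drug-related toxicity stay evaluable. The estimate free of this exclusion will therefore exist. What is missing is its designation as primary and its link to the stopping rule.
- Section 8.4 is the only section headed as analysis populations, and the Section 6 wording may be loose. That supports reading the evaluable set as primary, which is the reading that admits the bias.
- Replacement is discretionary, and the documents give no non-evaluable rate. CBCs are at least weekly for two cycles, so if blood results count as an assessment, exclusions could be few. The 20% figure is only a scenario.
- Because drug-toxicity discontinuations are retained, excluded patients probably carry less toxicity than the rest. That is closer to (b), where the joint false-go rate is flat or falls. The ORR is inflated all the same.
- At 24, not stopped is an interim status, which is not the same as acceptable.
- With 4-week cycles, the day 85–91 gap lies within the ±7-day laboratory window in 6.1.1 and 6.1.2. The 5- and 6-week cases do not.

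Naming the evaluable set as primary, with a stated replacement cap, would also remove the inconsistency, but not the upward bias.

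**Conclusion.** The concern holds and should be fixed. The primary ORR population is unreconciled, the set implied by 8.4.2 can only raise the ORR relative to all treated patients, and the two response windows conflict whatever is assumed.

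The size depends on an unknown non-evaluable fraction. At 10% to 20%, all non-responders, the ORR is inflated by about 2 to 5 percentage points in AML (22.2−20.0 to 25.0−20.0) and 2 to 4 in MDS (16.7−15.0 to 18.8−15.0). The effect on the joint false-go rate ranges from a small fall to a rise of about 8 points in AML (18.1−10.25) and 5 in MDS (14.7−9.25), depending on toxicity in the excluded patients. For a safe but inactive regimen the rise reaches about 13 points in AML (36.1−23.5) and 8 in MDS (31.1−23.0). These error rates assume full replacement, which would break the 30-patient cap, and null rates that refer to all treated patients.

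**What to change.** - In 8.4.2 and 8.5, name all Phase 2 patients who received at least one dose as the primary ORR set, and use the same set as the denominator for the stopping tables, up to 30 per arm.
- Count a patient with no assessment as a non-responder, and do not replace patients for efficacy.
- Keep the evaluable set as the sensitivity analysis, and state whether progression documented from blood is an assessment.
- State which denominator the 20% and 15% null rates refer to.
- Align the wording in 6.1.1 and 6.1.2 and the count that triggers the Phase 2 summary report.
- Give one response window, the same in 6.1.1, 6.1.2 and 8.0.

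No extra patients and no new analysis are needed, since both analyses are already planned. The replacement rule changes, so this is a protocol amendment and not only SAP wording. The reported ORR may be slightly lower.
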